## 17 APPENDIX D – IWCLL RESPONSE CRITERIA VERSION 2018

| GROUP | PARAMETER                       | CR   | PR  | PD   | SD   |
|-------|---------------------------------|--|---|--|--|
| A     | Lymph nodes                     | None $\geq$ 1,5 cm   | $\begin{array}{l} Decrease \geq 50\% \\ (from \ baseline)^{1)} \end{array}$ | Increase ≥ 50%
from baseline or
from response                  | Change of -
49% to
+49%  |
|       | Liver and/or
spleen size*    | Spleen size < 13
cm; liver size
normal                   | Decrease ≥ 50%
(from baseline)   | Increase ≥ 50%
from baseline or
from response                  | Change of -
49% to
+49%  |
|       | Constitutional
symptoms      | None   | Any   | Any  | Any  |
|       | Circulating
lymphocyte count | Normal   | Decrease ≥ 50%
from baseline   | Increase $\geq 50\%$
over baseline                                | Change of -
49% to
+49%  |
| В     | Platelet count                  | $\geq 100.000/\mu l$   | $\geq 100.000/\mu l \text{ or}$
increase $\geq 50\%$
over baseline    | Decrease of ≥
50% from
baseline
secondary to
CLL         | Change of -
49 to +49%  |
|       | Hemoglobin                      | ≥ 11,0 g/dl
(untransfused and
without
erythropoietin) | ≥ 11 g/dl or
increase ≥ 50%
over baseline                             | Decrease of $\geq 2$
g/dl from
baseline
secondary to
CLL | Increase <
11,0 g/dl or
< 50% over
baseline, or
decrease < 2
g/dl |
|       | Marrow                          | Normocellular, no
CLL cells, no B-
lymphoid nodules.     | Presence of CLL
cells, or of B-
lymphoid
nodules, or not
done   | Increase of CLL cells by $\geq$ 50% on successive biopsies           | No change
in marrow
infiltrate   |

 Sum of the products of 6 or less lymph nodes (as evaluated by CT scans and physical exam in clinical trials, or by physical exam in general practice).

**CR**, complete remission: all of the criteria have to be met; **PR**, partial remission: for a PR at least 1 of the parameters of group A and 1 parameter of group B need to improve if previously abnormal. If only one parameter of both groups A and B is abnormal prior to therapy, only 1 needs to improve. **PD**, progressive disease: at least one of the above criteria of group A or group B has to be met; **SD**, stable disease: all of the above criteria have to be met. Constitutional symptoms alone do not define PD.

\*Spleen size is considered normal if  $\leq$  13 cm. There is not firmly established, international consensus of the size of a normal liver; therefore, liver size should be evaluated by imaging and manual palpation in clinical trials and be recorded according to the definition used in a study protocol.

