# 8.3 IDENTIFICATION AND MEASUREMENT OF TUMOR LESIONS AND ORGANOMEGALY

#### 8.3.1 TARGET LESIONS

At baseline, up to 6 lymph nodes should be selected as target lesions (if measurable disease is present) that will be used to quantitate the status of the disease during study treatment. Ideally, the target lesions should be located in disparate regions of the body. Only peripheral nodes need be selected as target lesions. However, it is optimal if mediastinal and retroperitoneal areas of disease are assessed whenever these sites are involved.

Target lesions should be measured and recorded at baseline and as per the study assessment schedule. The cross-sectional dimensions (the largest cross-sectional diameter, i.e., the LD × LPD) will be recorded (in cm) for each target lesion. The product of the perpendicular diameters (PPD) (in cm^2) for each target lesion and the sum of the products (SPD) (in cm^2) for all target lesions will be calculated and recorded. The baseline SPD will be used as references by which objective tumor response will be characterized during treatment. The nadir LD of individual lesions and the nadir SPD will be used as references by which CLL progression will be characterized. All LD and LPD diameters will be reported in centimeters and all PPDs and SPDs will be reported in centimeters squared.

A nodal mass may be selected as a measurable nodal target lesion if it is > 1.5 cm in the longest diameter (Hallek M, 2018).

Progressive disease will be determined using the 2018 iwCLL criteria. Transient increases of lymph node size during treatment with novel inhibitors may occur (Hallek M, 2018).

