#### 8.4 DEFINITIONS OF TUMOR RESPONSE AND PROGRESSION

Responses will be categorized as CR, PR, SD, or PD. Response criteria for this protocol will be per iwCLL 2018 criteria (see Appendix D). Response to therapy includes 2 groups of parameters that need to be documented. Group A assesses the lymphoid tumor load (CT) and constitutional symptoms; group B assesses the hematopoietic criteria. The hemataopoietic criteria will be evaluated using the lab testing on Cycle 4 Day 1 and Cycle 13 Day 1.

For the purpose of this study, the bone marrow biopsy response criterion will be calculated using the following formula:

Cellularity x % involvement of CLL= percent of response

If the reporting pathologist provides a range for B-cell or lymphocytic leukemia involvement (i.e.,80-85%), the higher number of the range will be used for the calculation.

The best overall response will be determined. The best overall response is the best response recorded from the start of treatment until disease/recurrence progression (taking as a reference for disease progression the smallest measurements recorded since treatment started). Where imaging data are available, these data will supersede physical examination data in determining tumor status.

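### Appendix D scores an isolated lymphocyte rise of 50% or more as progression, which the protocol text excludes, so a responder can be scored PD for the primary endpoint

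*Combined protocol and SAP*

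**What the plan says.** Scoring rules:

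- Section 8.4: "Response criteria for this protocol will be per iwCLL 2018 criteria (see Appendix D"). Section 8.3.1: "Progressive disease will be determined using the 2018 iwCLL criteria".
- Appendix D, circulating lymphocyte count (a group A row), PD column: "Increase $\geq 50\%$ over baseline".
- Appendix D, PD rule: "progressive disease: at least one of the above criteria of group A or group B has to be met". The only exemption given is "Constitutional symptoms alone do not define PD".
- Appendix D, PR rule: "for a PR at least 1 of the parameters of group A and 1 parameter of group B need to improve if previously abnormal".
- Section 8.4 takes best overall response as the "best response recorded from the start of treatment until disease/recurrence progression".

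Text on lymphocytosis:

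- The PFS definition under Efficacy Endpoints and Section 9.7 both define definitive progression by the 2018 iwCLL criteria, for any reason except lymphocytosis.
- Section 8.5 says that a temporary rise of at least 50% from baseline, to above 5,000/mcL, may occur on umbralisib and usually resolves in three to four months. It keeps such patients on drug until progression shows in some other sign, or until another reason to stop arises.
- Section 8 keeps responders on drug until definitive progression.

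Decisions that depend on the score: ORR (CR + PR) is primary (Section 2.1). Section 9.1 stops the trial at 18 or fewer responses in 27 and calls it positive at 25 or more in 35. Section 4.4 takes patients off treatment if they have no PR or CR at the Cycle 3 assessment.

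**The concern.** The scoring table and the protocol text give opposite answers for the same finding, a lymphocyte rise of 50% or more without other worsening. The threshold in the PD cell is the size of rise that Section 8.5 attributes to the drug. Appendix D does list an exemption from PD, and lymphocytosis is not in it, so an investigator scoring from the table has no prompt to set the rise aside.

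Patients who meet the PR rule and also have the rise are the ones at risk. Scored literally as PD, such a patient is lost from the ORR numerator and counts against both Simon boundaries. The patient also comes off a drug that Section 8.5 would continue. Patients whose only change is a lymphocyte rise are non-responders on either reading.

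**Working it through.** **1. One patient under each rule.** Take nodes down 60% from baseline, one abnormal group B value improved, and lymphocytes up at least 50%, with nothing else worse.

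- Appendix D PR rule: one group A parameter (nodes) and one group B parameter have improved, so PR is met. The rule does not require the lymphocyte count to fall.
- Appendix D PD rule: one group A criterion (lymphocytes) is enough, so PD is also met. The table does not say which prevails.
- With the exclusion from Sections 8.5 and 9.7 applied, the PD criterion drops out and the patient is PR.

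**2. Timing.** The Cycle 3 assessment falls within the 14 days before Cycle 4 Day 1. Three 28-day cycles are 84 days, and 84 / 30.44 = 2.8 months. Section 8.5 expects resolution at three to four months, so the rise may still be present. One limit applies: Section 8.4 says "group B assesses the hematopoietic criteria" and ties those to the Cycle 4 Day 1 laboratory draw, but Appendix D places the lymphocyte count in group A. The date of the deciding lymphocyte reading is therefore not fixed.

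**3. The plan's own design.** Inputs from Section 9.1: n1 = 27, stop at 18 or fewer; n = 35, success at 25 or more; p0 = 0.60, p1 = 0.80.

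P(success | p) = sum over x = 19 to 27 of P(X1 = x) × P(X2 ≥ 25 − x), with X1 ~ Bin(27, p) and X2 ~ Bin(8, p).

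This gives 0.0965 at p = 0.60 and 0.9003 at p = 0.80, which agrees with the stated error rates of 0.10.

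**4. Margin.** At p = 0.80 the expected number of responders is 35 × 0.80 = 28, against 25 needed. Four of those 28 rescored leaves 24, a negative trial. In stage 1, 27 × 0.80 = 21.6 are expected against 19 needed.

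**5. Illustration.** Let f be the assumed share of true responders rescored as PD. The observed response rate is p = 0.80 × (1 − f).

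| f | p | P(success) | P(stage 1 stop) |
|---|---|---|---|
| 0 | 0.80 | 0.900 | 0.074 |
| 2.5% | 0.78 | 0.839 | 0.120 |
| 5% | 0.76 | 0.760 | 0.179 |
| 10% | 0.72 | 0.567 | 0.334 |
| 15% | 0.68 | 0.367 | 0.513 |
| 20% | 0.64 | 0.204 | 0.682 |

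Success probability is 0.80 at f = 3.8% and 0.50 at f = 11.6%. If the share s is taken of all patients instead, p = 0.80 − s: s = 5% gives 0.715 and s = 10% gives 0.465.

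The documents give no value for f. Section 1.2.2.1 reports PR with lymphocytosis in 7 of 20 Phase I CLL patients. That is not used as an estimate, because those patients had relapsed or refractory disease and neither the size nor the timing of the rise is given.

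**The case against.** The strongest reply is that the intended rule is clear. Section 9.7 sits in the efficacy analysis, lists progressive disease as a category, and takes definitive progression from the 2018 iwCLL criteria with lymphocytosis excepted. Appendix D is headed as those same criteria, so Section 9.7 can be read as modifying the table. Section 8.5 is specific to this drug effect and should outrank a generic cell. On that reading f = 0 and power stays at 0.900. The illustration would then show only that a 27/35 design is sensitive to any lost responders. The full 2018 guideline, which Section 9.9.1 cites for ORR, might also deal with lymphocytosis; that cannot be checked from these documents.

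Much of this stands. The text favours the exclusion, PFS and DOR are already protected by their use of definitive progression, and the size of f is unsupported.

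It does not remove the contrary rule from the table that scorers are told to use. Section 9.7 does not mention Appendix D and names best response and progression as separate determinations. Section 8.4 adopts the table without the exclusion and closes the best-response window at progression, without the qualifier definitive. Nor does Section 8.5 protect a patient scored PD: it lets treatment stop for another reason, and lack of PR or CR at Cycle 3 is one under Section 4.4.

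**Conclusion.** The point holds and should be fixed. As written, Appendix D gives a wrong primary-endpoint call for a patient who meets the PR rule and has a lymphocyte rise of at least 50%. It can also take that patient off treatment at Cycle 3. The effect is confined to response category, best overall response, ORR with its two boundaries, and the Cycle 3 decision.

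How many patients this would touch is unknown, and the illustrative losses assume that every such patient is scored literally as PD. What the figures do establish is that the margin is thin: rescoring about 4% of responders brings the success probability down to 0.80. Confidence is medium, because the text elsewhere shows the intended rule and investigators may well apply it.

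**What to change.** 1. In Appendix D, add to the PD rule and to the lymphocyte PD cell that isolated lymphocytosis on umbralisib, as described in Section 8.5, does not define PD.
2. In Section 8.4, state that this governs response category, best overall response, PFS, DOR and the Cycle 3 decision. State also that a patient who otherwise meets the Appendix D PR rule is scored PR despite lymphocytosis, for ORR and for both Simon boundaries.
3. Optional: report ORR with its exact 95% confidence interval with and without these patients, as a sensitivity analysis.

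The cost is a wording amendment to Appendix D and Section 8.4, plus one table if the optional analysis is done. Lymphocyte counts and CT data are already collected, and the sample size and boundaries do not change. The rule should be in place before responses are scored, because this is a single-arm trial in which the treating investigator makes the call.
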